# **Background and Rationale**

An important component in the pre-operative patient evaluation is to establish the duration of time a patient has been fasting in order to reduce the risk of pulmonary aspiration. An inadequate fasting time may prompt a change in anesthetic plans or result in the delay or cancellation of a case altogether. The risk of anesthetic-related pulmonary aspiration is rare due to current anesthetic practices, with the incidence in adults cited around 0.05% or less. However, the sequelae of aspiration can lead to aspiration pneumonitis, prolonged mechanical ventilation and unanticipated intensive care.

There is no established gastric volume definitively known to increase anesthetic risk of aspiration but it has been observed that the gastric volume in most healthy, fasted patients can be up to 1.5 ml/kg.

Current guidelines recommend a minimum fasting period of 8 hours for fatty foods, 6 hours for nonhuman milk and non-fatty solid foods, and 2 hours for clear liquids. Acceptable examples of clear liquids include water, black coffee or tea, carbonated beverages, and fruit juices without pulp. However, about 68% of adults in the United States consume coffee with add-ins such as cream and/or sugar. One study by Larsen et al. found that adding up to 50% full fat milk to coffee led to no or minimal increase in gastric volume measured by Magnetic Resonance Imaging after 2 hours. Hillyard et al.8 examined the addition of milk to tea and found no difference in gastric emptying times using the paracetamol absorption technique and ultrasound measurement of the gastric antrum. These studies provide some useful insight on gastric emptying times but are not generalizable to beverage consumption in the United States. Typically, the volume of coffee consumed is larger than that in Europe and half and half is preferred to milk. Half and half is a mixture of milk and cream and has a fat content ranging from 10.5-18% compared to 3.25% fat in whole milk.9 Non-dairy coffee creamer is another popular addition to coffee, which consists of vegetable oil and corn syrup. This adds both fat and sugar to coffee. Therefore, the effects of larger quantities of coffee with the addition of high fat content milk products on gastric emptying is unknown. We propose a volunteer cross-over study in healthy individuals to assess the effects of milk additives to coffee and its effects on gastric emptying. In this study we will compare two separate additions to the coffee using half and half and liquid non-dairy coffee creamer.

## **Objectives**

The primary objective of this study is to compare gastric volume using bedside ultrasound in volunteers 2 hours after consumption of black coffee, coffee with half and half, and coffee with non-dairy creamer.

PI: [name]

## Study Design and Procedures (sometimes called "Methods")

This study is a randomized controlled crossover study with 3 arms. One arm is the consumption of a 12 ounce (354.8 ml) brewed black coffee. The second is a 12 ounce brewed black coffee plus 1 ounce (30 ml) of half and half. The third arm is a 12 ounce brewed black coffee plus 1 ounce (30 ml) of non-dairy coffee creamer. Each subject will participate in all 3 arms of the study and serve as their own control.

The order of which arm they will be assigned to will be determined by a computerized random number generator which will create a unique sequence from 1 to 3. The number 1 will be attributed to black coffee without additives. The number 2 will be attributed to coffee with half and half and the number 3 will be attributed to coffee with non-dairy coffee creamer. For example, a random generation of the sequence 2 1 3 will result in the order of arms to be coffee with half and half, black coffee, then coffee with non-dairy creamer. The investigator performing the gastric ultrasound will be blind as to which drink was consumed. In order to maintain blinding and anonymization during the study, each participant will be assigned a unique study number which will not be associated with any identifying information. This study number will be associated with the randomized number sequence of their coffee arm order and will be used each time the participant returns for the next study measurement.

Each study participant will be instructed to consume nothing by mouth for at least 6 hours prior to the commencement of the study. An investigator will measure the cross-section of the gastric antrum using bedside ultrasound with the participant in the right lateral decubitus position as a baseline measurement. The participant will then consume one of the 3 prepared coffee options. They will be instructed to return 2 hours post consumption for the investigator to repeat the gastric antrum cross-section measurement with ultrasound. There must be a minimum of 2 days between repeat measurements with the other arms of the study.

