## **Study Population**

The study population will be composed of volunteers between the ages of 18 and 65 and will include 30 total subjects. Recruitment will be via an email to the Department of Anesthesia at the University of Arkansas for Medical Sciences asking for volunteers to participate in the study. In order to minimize coercion, it will be emphasized that participation is voluntary and that there is no reward or negative consequence for participating or not. A total of 2 reminder emails will also be sent 1 week apart from each other and the initial recruitment email. No recruitment will occur in person to avoid potential pressure from a colleague/peer.

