# **Data Analysis**

Point of care bedside ultrasound will be used to measure the cross-sectional area of the gastric antrum of participants at baseline prior to consumption of coffee and 2 hours after consumption of coffee. Three measurements will be taken and recorded each time and the mean of these measurements will be used to calculate the predicted gastric volume. The difference between gastric volume at baseline and after coffee consumption will be compared across all three study arms. We will analyze the data using standard statistical methods such as mean, median, mode, standard deviation and statistical significance. We will also determine if the gastric volumes after consumption of coffee in each arm exceeds 1.5 ml/kg.

PI: [name]

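### Drink order is randomized with no stated balancing over the six possible orders, and the analysis names no session (period) term, although 30 participants allow five per order and session number is recorded

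*Combined protocol and SAP*

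**What the plan says.** - **Design.** Study Design and Procedures: "This study is a randomized controlled crossover study with 3 arms". Every participant takes all three drinks.
- **Order.** The same section takes the order from "a computerized random number generator which will create a unique sequence from 1 to 3". Its example shows that an order is a full permutation: "a random generation of the sequence 2 1 3 will result in the order of arms to be coffee with half and half, black coffee". No block, Latin square or quota per order is stated, and the text does not say how the list across participants is made. The word unique cannot supply a balancing rule. Only six orders exist for 30 people, so orders must repeat, and the natural reading is that no number repeats within one sequence.
- **Spacing.** "There must be a minimum of 2 days between repeat measurements with the other arms of the study".
- **Sample size.** Study Population: the study "will include 30 total subjects".
- **Outcome.** Objectives: to "compare gastric volume using bedside ultrasound in volunteers 2 hours after consumption". Data Analysis: "The difference between gastric volume at baseline and after coffee consumption will be compared across all three study arms". That section also checks 2-hour volumes against 1.5 ml/kg.
- **Method.** "We will analyze the data using standard statistical methods such as mean, median, mode, standard deviation and statistical significance". No model is named, and no session, period or sequence term.
- **Data collected.** The data collection form in the Appendices has a Session # column.

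**The concern.** Each participant is measured on three occasions at least two days apart. If the outcome drifts from one session to the next, a drink that happens to be taken late more often than another picks up part of that drift. Two standard devices deal with this. Balancing the orders makes every drink fall equally often in each session, and a period term removes the drift from the error. The plan states neither, though the sample size divides exactly by the number of orders and session number is already collected.

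What is at stake is precision. Chance imbalance does not bias the drink contrasts on average and does not inflate type I error. How exposed the trial is depends on the outcome. For change from baseline, a shift that affects both scans of a session equally cancels, so only drift in the change itself matters. For the 2-hour volume in the Objectives, and for the 1.5 ml/kg check, there is no such cancellation.

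**Working it through.** **Inputs.** From the documents: 3 drinks, 3 sessions and 30 participants. The documents give no alpha, power, effect size, SD or session drift, and no derivation of the 30, so there is no planned figure to reproduce. Assumptions: orders drawn independently with probability 1/6 each; a 5% test; complete data; linear drift of d = 0.1, 0.25 or 0.5 per session, in units of the within-person SD of the analysed outcome.

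**Step 1: is balance available?** There are 3! = 6 orders, and 30/6 = 5 per order. Each drink comes at a given position in two of the six orders, so it would be taken 2 × 5 = 10 times in each session.

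**Step 2: how likely is balance by chance?** Multinomial probabilities:
- Five in every order: 30!/((5!)^6 × 6^30) = 0.00040, or 0.04%.
- Each drink first for exactly 10 people: 30!/((10!)^3 × 3^30) = 0.0270, or 2.7%.
- Some order with two or fewer people: 53%.
- Some drink given first to 6 or fewer, or 14 or more, people: 36%.

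These describe imbalance in counts. The cost in precision follows.

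**Step 3: variance of a drink contrast.** With balanced orders and a period term it is 2/30 = 0.0667 (SD 0.258). With independent orders and no period term, each participant's contrast also carries d times the difference in session position of the two drinks. Over the six orders that difference is ±1 four times and ±2 twice, so its mean square is (4 × 1 + 2 × 4)/6 = 2. The variance becomes 2/30 + 2d²/30 = (2/30)(1 + d²).

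| d | Variance ratio | SD of contrast |
|---|---|---|
| 0.1 | 1.01 | 0.259 |
| 0.25 | 1.0625 | 0.266 |
| 0.5 | 1.25 | 0.289 |

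**Step 4: period term with unbalanced orders.** Least squares with participant, drink and session effects, over 20,000 simulated allocations, gives a mean variance about 3.7% above the balanced value, whatever the drift. The 95th percentile is 9% when the three contrasts are averaged and about 11% for a single contrast.

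**Step 5: balance without a period term.** Drift then cancels from the contrasts but stays in the residual. The session sum of squares is 30 × (1 + 0 + 1) × d² = 60d², so the expected residual mean square is inflated by (58 + 60d²)/58 = 1.01, 1.06 and 1.26. The test becomes conservative.

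**Step 6: power and type I error.** Simulation with 20,000 trials per cell, participant effects removed, overall F test. For power, one drink is shifted by 0.713 within-person SD, which gives 80% power with both changes.

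| | d = 0.1 | d = 0.25 | d = 0.5 |
|---|---|---|---|
| Power, neither change | 79.5% | 77.8% | 69.9% |
| Power, balance only | 79.8% | 77.8% | 70.1% |
| Power, period term only | 79.0% | 78.6% | 78.3% |
| Power, both changes | 79.9% | 79.9% | 80.4% |
| Type I error, neither change | 4.9% | 4.7% | 5.0% |
| Type I error, balance only | 4.8% | 4.2% | 2.4% |

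The Monte Carlo standard error is about 0.3 points for power, √(0.8 × 0.2/20,000), and about 0.15 points for type I error. A separate set of 20,000-trial runs gave 79.6%, 77.5% and 69.6% for power with neither change, and type I errors of 4.8%, 4.0% and 2.5% with balance only.

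**The case against.** The strongest reply is that nothing here is invalid. Orders are random, each participant is their own control, the sonographer is blinded and sessions are spaced. The protocol does not say how the list is made, so a balanced list is not ruled out, and every probability in Step 2 depends on independent draws. The cost depends on a drift that no passage reports. At d = 0.1 it is negligible, and d = 0.5 means a full within-person SD between the first and third sessions. Change from baseline already removes any shift common to both scans. Balance alone recovers almost no power. A period term alone costs about 3.7% in variance when orders are unbalanced, so it pays only above roughly d = √0.037 = 0.19. The missing period term is also part of a larger gap, since no model is named. Exact balance needs all 30 volunteers to finish three sessions.

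Most of this stands, and it is why the point is minor. It does not remove the point. The weakness of each change alone is the reason to make both: balance removes the variance cost of the period term, and the period term removes the conservatism that balance brings. With both, power was about 80% at every drift tested. Change from baseline does not protect the 2-hour volume or the 1.5 ml/kg check. Dropout loosens exact balance but does not undo it, and a mixed model with a session term handles what remains. If a balanced list is already intended, one sentence settles that half, and the session term is then needed more.

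**Conclusion.** The concern holds, as a minor point of efficiency. The plan states no balancing of drink orders and no session term, although five participants per order is available and session number is collected. Under independent draws and linear drift of 0.1, 0.25 or 0.5 within-person SD per session, the variance of a drink contrast is 1%, 6% or 25% higher than it need be. Power falls from 80% to about 80%, 78% or 70%. There is no average bias and no inflation of type I error.

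The result rests on the assumed drift range and on independent draws. It also rests on an analysis that removes participant effects, which the Data Analysis section does not state. If the analysed outcome does not drift, almost nothing is lost either way.

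**What to change.** Make two changes together.

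1. **Study Design and Procedures:** allocate from a pre-generated list of five blocks of six. Each block contains all six orders of 1 to 3 once, in random sequence, which gives five participants per order and each drink 10 times in each session. Keep the list from the investigators who perform the scans.
2. **Data Analysis:** state the primary model, with drink and session number as fixed effects and participant as a random effect.

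The list must exist before the first participant is allocated, because balance cannot be restored afterwards. The cost is one list and one model term, which takes two residual degrees of freedom: 90 − 30 − 2 = 58 becomes 56 with complete data. No participants, visits or data items are added.

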# Data Handling and Recordkeeping

The Principal Investigator will carefully monitor study procedures to protect the safety of research subjects, the quality of the data and the integrity of the study. De-identified data will be initially recorded on paper on a data collection form then transcribed to Excel and kept on UAMS-maintained servers. The paper records will be destroyed by confidential shredding. All collected data will be completely anonymized with no way to relink it to individual participants. Each participant will be assigned a unique study number which will not be associated with any identifying information. This study number will be used each time the participant returns for the next study measurement. Only investigators will have access to the collected data. At the conclusion of the study, the data which is permanently de-identified will be retained for seven years after completion of the project.

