# Study: How do you take your coffee before anesthesia? Data Collection Form

Date: \_\_\_\_\_

ID #	Session #	Age	Gender	Height	Weight	BMI	Time coffee consumed	Time US exam	Baseline Antrum CSA			Post coffee Antrum CSA

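### The operator is blinded to the drink but not to the session's baseline reading, which shares a form row with the 2-hour reading: an avoidable risk of measurement bias, of unknown size and uncertain direction

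*Combined protocol and SAP*

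**What the plan says.** The only masking in the Study Design and Procedures section concerns the drink: "The investigator performing the gastric ultrasound will be blind as to which drink was consumed". For the fasting scan, "An investigator will measure the cross-section of the gastric antrum using bedside ultrasound with the participant in the right lateral decubitus position". For the second scan, participants are told when to come back: "They will be instructed to return 2 hours post consumption for the investigator to repeat the gastric antrum cross-section measurement with ultrasound". The change of article and the word for repeating suggest one operator for both scans, but the protocol does not say so outright. Ethical Considerations refers only to one of the study investigators.

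Under Data Handling and Recordkeeping, "De-identified data will be initially recorded on paper on a data collection form then transcribed to Excel". The single form in the appendix has one header row. It carries the ID and session number together with "Baseline Antrum CSA" and "Post coffee Antrum CSA", so one row per participant and session appears intended. The form has no column for the drink.

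Data Analysis says "Three measurements will be taken and recorded each time and the mean of these measurements will be used to calculate the predicted gastric volume", and defines the comparison: "The difference between gastric volume at baseline and after coffee consumption will be compared across all three study arms". It also sets each arm's post-coffee volumes against 1.5 ml/kg.

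No section covers the baseline values at 2 hours, assigns a separate recorder, or provides for stored images or blinded re-reading.

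**The concern.** Antral area depends on what the operator outlines. The analysed quantity is the difference between two such readings, and the plan leaves the first open to view while the second is made. Blinding to the drink stops an operator from favouring one drink. It does not stop an operator from being drawn toward a value already on the page, or toward an expectation about the time point. Averaging three readings reduces random error but not a pull that all three share.

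At stake are the estimated millilitre differences between drinks and the number of volumes above 1.5 ml/kg. The Background contrasts a 6-hour fasting period for nonhuman milk with 2 hours for clear liquids, so an understated effect of the additives would matter to a reader of the results.

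**Working it through.** The plan has no figure to reproduce on this point. It gives no expected volumes, reading error, effect size, SD, significance level or power, and its sample size of 30 has no derivation.

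**Inputs from the documents:** 30 participants, each taking all three drinks; three readings averaged per time point; change from baseline as the compared quantity; a 1.5 ml/kg cutoff.

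**Assumed inputs:** a uniform pull *a* of 10%, 20% or 30%; a true between-drink difference of 30 ml; 70 kg body weight; a paired t-test at two-sided 5%.

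**1. Pull toward baseline.** Let B be the recorded baseline volume, P the 2-hour volume an operator unaware of B would have recorded, and D = P − B. Suppose the recorded value is P* = (1 − a)P + aB. Then:

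- Recorded change: P* − B = (1 − a)D.
- Recorded difference between drinks: (1 − a)(D1 − D2).
- With D1 − D2 = 30 ml: 0.9 × 30 = 27, 0.8 × 30 = 24, 0.7 × 30 = 21 ml.

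This is written on the volume scale. A pull on area carries over exactly only if the conversion to volume is linear in area for a given participant, and the plan does not state the conversion.

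**2. The test on change.** With d the paired difference in change, t = mean(d) / (SD(d)/√30). A uniform *a* multiplies mean and SD by the same (1 − a), which cancels, so the p-value is unchanged.

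In power terms, an effect with 80% power at n = 30 has a standardised paired difference of 0.53. Under the uniform pull it stays 0.53 and power stays at 80%. Only if the mean shrinks while the SD does not does it fall:

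| a | 0.53 × (1 − a) | Power |
|---|---|---|
| 10% | 0.477 | 71% |
| 20% | 0.424 | 61% |
| 30% | 0.371 | 50% |

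Nothing in the documents supports that extra assumption.

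**3. The 1.5 ml/kg count.** Under the same model P* − P = −a(P − B). The reading falls when P exceeds B and rises when P is below B. Because P* lies between P and B, a volume can cross the cutoff upward only if B is above it. At 70 kg the cutoff is 1.5 × 70 = 105 ml. With an illustrative baseline of 40 ml and a = 20%, a volume is recorded below the cutoff when 0.8P + 8 < 105, that is P < 121.25 ml. Volumes from 105 to about 121 ml would then be missed.

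A 20,000-replicate simulation used an assumed mean baseline of 40 ml, a mean 2-hour volume of 65 ml in the drink counted, and assumed SDs. The share above 105 ml fell from 18% to about 12–13% at a = 20%.

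**4. A different bias.** Suppose the operator expects a fuller stomach after any drink and reads high by a constant k in every arm. The difference between drinks is (D1 + k) − (D2 + k) = D1 − D2, which is unchanged. The count above 1.5 ml/kg can then only rise or stay the same.

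**The case against.** The strongest reply is that the exposure is inferred. The documents do not say who writes on the form or whether the person scanning sees it, and one operator for both scans is a plausible reading rather than a stated fact. That stands. It limits the point to what the plan permits: the operator can have the baseline in view, and nothing prevents it.

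A second reply is that randomised order, within-person comparison and drink blinding already protect the comparison. They do guard against favouring one drink, and the form does not reveal the drink. They do not keep the estimates free of a bias common to all arms.

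A reader might infer that the bias must run toward no difference, or that it would produce a falsely non-significant result. The documents support neither reading. The direction in step 1 comes from the chosen equation, and step 4 gives an equally possible mechanism with a different effect. Under the uniform pull the test on change does not move, and the plan sets no margin or equivalence test against which a shrunken estimate would be judged. A reader might also infer that a null result would be used to relax fasting advice, but Dissemination of Data mentions only presentations, posters and publications.

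**Conclusion.** The point holds as an avoidable risk of measurement bias common to all arms. Followed as written, the plan lets an operator-determined outcome be read with that session's baseline on the same row.

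If readings are pulled toward baseline, estimated changes and between-drink differences shrink by (1 − a). The 1.5 ml/kg count can shift, mostly downward if, as the Background suggests, most fasting volumes lie at or below the cutoff. If expectation drives readings up, the count is inflated and drink differences are largely unaffected.

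The 30 ml and 10–30% figures illustrate scale only, because the documents give no value for either. The unchanged p-value rests on a uniform proportional pull and on the comparison of changes. The point does not show that the results would be wrong or that the trial would lose power. It justifies a cheap improvement before data collection.

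**What to change.** Split the form in two. The baseline sheet is handed in before the participant leaves. The 2-hour sheet carries ID, session and times but no baseline values. Add a sentence to Study Design and Procedures stating that the operator is blind to the drink and does not consult that session's baseline readings, and say there who scans and who records.

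Optionally, the same investigators save unlabelled stills and trace them later in random order, blind to drink and time point. This addresses both anchoring and expectation at the tracing step.

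The cost is a revised form and a little protocol text, with no extra scans, visits or staff. Tracing stills adds some investigator time. Separate sheets reduce recall but do not remove it, and later tracing still leaves image capture with someone who knows the time point. The change has to come before data collection, because without stored images the readings cannot be re-made afterwards.

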## **Exclusion Criteria**

• History of diabetes, delayed gastric emptying, previous gastric surgery, lactose intolerance, currently pregnant, consumption of solid/liquids in 6 hours prior to commencement of ultrasound study

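### Cheap improvement: sessions may start 6 hours after a fatty meal although the background cites 8 hours, and last intake is not recorded, which could add some noise to the change score

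*Combined protocol and SAP*

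**What the plan says.** The Study Design and Procedures section sets one rule for every session: "Each study participant will be instructed to consume nothing by mouth for at least 6 hours prior to the commencement of the study". The Exclusion Criteria repeat the same interval: "consumption of solid/liquids in 6 hours prior to commencement of ultrasound study". Neither separates fatty from other food.

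The Background and Rationale section reports guideline intervals that do make this distinction: "a minimum fasting period of 8 hours for fatty foods", 6 hours for non-fatty solids and nonhuman milk, and 2 hours for clear liquids.

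Each session has a baseline antral scan, the drink, and a second scan 2 hours later. On the readings, the Data Analysis section says: "Three measurements will be taken and recorded each time". On the comparison, it says: "The difference between gastric volume at baseline and after coffee consumption will be compared across all three study arms". The primary objective is worded differently, as a comparison of the post-drink volume itself: "to compare gastric volume using bedside ultrasound in volunteers 2 hours after consumption".

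The Data Collection Form has a column headed "Time coffee consumed" and one for the time of the ultrasound exam. The listed columns include none for the time or content of the last meal or drink.

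**The concern.** The baseline scan is one half of the change score. If a participant arrives 6 to 8 hours after a fatty meal with some food still in the stomach, and it empties before the second scan, that session's change is too low by the volume cleared. Subtracting the baseline does not remove this transient residue; it brings it into the outcome.

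The scan would reveal a markedly full stomach but not a small residue. The background notes that "the gastric volume in most healthy, fasted patients can be up to 1.5 ml/kg", so a residue of a few tens of millilitres looks like ordinary fasted content. With no record of the last intake, neither its cause nor compliance with the fast could be checked later.

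What is at stake is precision in one planned comparison. Randomised drink order means the residue has the same expected effect under each drink.

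**Working it through.** **Timing.** The gap between the cited guideline and the rule is 8 − 6 = 2 hours. The second scan falls at least 6 + 2 = 8 hours after any permitted food. The 2-hour volume and the 1.5 ml/kg check use only that scan, so no effect on them is claimed.

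**Can the baseline scan identify it?** At an assumed 70 kg, 1.5 ml/kg is 1.5 × 70 = 105 ml. An assumed residue of 20 to 40 ml is 20/105 = 19% to 40/105 = 38% of that, which lies within ordinary fasted variation.

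**Inputs for the illustration.** From the protocol: 30 participants and three arms, so 30 × 3 = 90 sessions. The protocol gives no SD, effect size, alpha, power or residue volume, so there is no figure of its own to reproduce. Assumed:
- p, share of sessions with residue: 0.05 to 0.20 (4.5 to 18 of the 90 sessions)
- r, volume cleared by the second scan: 20 to 40 ml
- s, change-score SD per session without residue: 30 ml (range 20 to 40), independent between a participant's sessions
- c, within-person correlation of residue: 0 or 0.5
- two-sided alpha 5%, 80% power, paired t test of two drinks

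**Formulas.**
- Shift in each arm's mean change = p × r, downward and equal in all arms: 0.05 × 20 = 1 ml to 0.20 × 40 = 8 ml.
- Residue variance v = p(1 − p)r²: 0.0475 × 400 = 19; 0.09 × 900 = 81; 0.16 × 1600 = 256 ml².
- SD of a paired difference = √(2(s² + v(1 − c))). Without residue, at s = 30, this is √1800 = 42.43 ml.
- Effective n = 30 × s² / (s² + v(1 − c)).
- Detectable difference from the noncentral t distribution with n = 30. Without residue it is 22.45 ml.

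**Results at s = 30 ml.**

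| p, r | c | SD of difference (ml) | Rise | Effective n | Detectable difference (ml) |
|---|---|---|---|---|---|
| 5%, 20 ml | 0 | 42.87 | 1.0% | 29.4 | 22.69 |
| 5%, 20 ml | 0.5 | 42.65 | 0.5% | 29.7 | 22.57 |
| 10%, 30 ml | 0 | 44.29 | 4.4% | 27.5 | 23.44 |
| 10%, 30 ml | 0.5 | 43.37 | 2.2% | 28.7 | 22.95 |
| 20%, 40 ml | 0 | 48.08 | 13.3% | 23.4 | 25.45 |
| 20%, 40 ml | 0.5 | 45.34 | 6.9% | 26.3 | 24.00 |

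If residue were identical in all of a person's sessions (c = 1), it would cancel and there would be no increase.

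**Range over s.** The smallest rise is at s = 40, v = 19, c = 0.5: √(1 + 9.5/1600) = 1.003, or 0.3%. The largest is at s = 20, v = 256, c = 0: √(1 + 256/400) = 1.281, or 28%. With c = 0.5 that last case falls to √(1 + 128/400) = 1.149, or 15%.

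**Cross-check by a second route.** Express the residue noise as a fraction of the change-score SD and use a normal approximation. Fractions of 0.1, 0.2 and 0.3 multiply the SD by 1.005, 1.020 and 1.044, and power falls from 80% to 79.6%, 78.4% and 76.5%. The mid case above with c = 0 has 81/900 = 0.09 = 0.3², so it matches the last of these.

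**The case against.** The 8-hour figure is a safety interval for patients about to be anaesthetised. These are volunteers being scanned, and nothing in the protocol says a valid baseline needs 8 hours. The 6-hour rule matches the cited interval for non-fatty solids and milk. It is also a minimum, and how often anyone would start 6 to 8 hours after a fatty meal is unknown. This stands: the rule is a different choice from the cited guideline, not a contradiction within the protocol.

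The design already absorbs much of the problem, through a baseline scan with three readings in every session, within-person comparison and randomised order. This also stands, and it is why only noise is claimed.

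The numbers rest wholly on assumptions, and two modelling steps lean towards a larger effect. If the assumed SD already includes ordinary fasted variation, some residue is counted twice. Residue that had not cleared by the second scan would largely cancel in the change score; it would then count in the post-coffee volume, an effect not claimed here. Both points are fair. For the change score they shrink an effect that is already described as possibly zero.

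Finally, fatty food is undefined and self-reported, and rescheduling could cost sessions in a 30-person, three-visit study. That cost is real but should be small, and it can be limited by giving participants examples of fatty meals in the instructions.

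**Conclusion.** The point holds as a minor, inexpensive improvement. The protocol permits a baseline scan 6 to 8 hours after a fatty meal, the form as listed could not show that this had happened, and the baseline enters a planned comparison. The consequence is possible extra noise in the change score and an equal expected lowering of the mean change in every arm, with no expected bias between drinks.

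The size is not known. In the assumed mid case the detectable difference goes from 22.45 ml to 22.95 or 23.44 ml, a loss of 0.5 to 1.0 ml. The 28% upper end needs the most unfavourable value of every input at once and should not be read as likely. Confidence is medium, because residue frequency, residue volume, clearance by the second scan and the change-score SD are all assumed.

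**What to change.** In Study Design and Procedures and in the Exclusion Criteria, keep the 6-hour rule for all intake and add that no fatty food may be eaten in the 8 hours before each session. Add two fields to the Data Collection Form, time of last intake and type of last intake, completed before the baseline scan. Reschedule any session that does not meet the rule. No separate sensitivity analysis is needed.

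The cost is one clause in two places, two form fields, a slightly stricter fast for volunteers and a few rescheduled sessions.
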